Upneeq[™] is an FDA approved drug for the treatment of ptosis. It is available in a drop formulation. This agent should be considered exempt from IND requirements as the study is using the drug in realm of FDA indications and meets the below IND criteria.

• The research is not intended to be reported to the FDA as a well-controlled study in support of a new indication for use nor intended to be used to support any other significant change in the labeling for the drug.

• The research is not intended to support a significant change in the advertising for the product.

• The research does not involve a route of administration or dosage level or use in a patient population or other factor that significantly increases the risks (or decreases the acceptability of the risks) associated with the use of the drug product.

• The research is conducted in compliance with the marketing limitations described in 21 CFR §312.7.

Drug insert is available and attached to the IRB protocol.

Procedures Involved

We anticipate that procedures listed below will take about 30 to 40 minutes per patient. Except as noted, the procedures below are not considered standard of care and are being conducted for the study alone.

Part 1: Pre-treatment data collection

- Patients will complete a pre-treatment survey to evaluate the perceived baseline eye appearance.
- Patients will undergo pre-treatment baseline photography. Images will be taken in a room with the same conditions.
- An Ipad (Apple Inc, Cupertino, California, U.S.A.) with the Upneeq software app will be used. This app directs subjects to a standardized position and distance from the Ipad to measure the MRD1 and MRD2 in each eye. The subjects will focus on the Ipad with their eyes in primary gaze.
- All photographs will be taken with the dedicated Ipad camera, which will use standardized aperture, shutter speed, and exposure time.
- Photographs will be recorded and saved as JPG files (1200 9 797 pixels, 24-bit, RGB) in a locked folder. When not in use, the Ipad and accompanying software will be secured in a locked drawer.

Part 2: Upneeq[™] application

- Subjects will be randomized to receive either Upneeq[™] or balanced saline placebo in both eyes.
- Based on the randomization results, the examiner will apply Upneeq[™] eye drops or saline to the subject's eyes.

Part 3: Post-treatment data collection

- Subjects will wait 2 hours after they receive eye drops.

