- Subjects will be photographed at 2 hours after drop instillation according to the procedure described above. This will allow Upneeq to reach its average time for maximum effect.
- Patients will complete a post-treatment survey to evaluate the perceived change in eye appearance following Upneeq[™] administration.

Part 4: Data analysis

- Data will be recorded and stored in a secure Microsoft Office Excel (Microsoft Corporation, Redmond, WA, U.S.A.) spreadsheet. Data will be graphically analyzed and represented with Adobe Photoshop (Adobe, Inc., San Jose, CA, U.S.A).
- Data assessed will involve assessing pre and post-treatment MRD1 and MRD2, investigator-assessed measurements of conjunctival color including the Validated Bulbar Redness Scale and patient-reported outcome measures such as those measured through the FACE-Q survey or other patient perceptions of the drop and changes in appearance before and after drop instillation.
- User performing analysis will be blinded to which patients received study drug or control.

No additional follow-up outside of the patient's next routine clinic visit will be needed. Patients who do have symptoms concerning any post-procedural complications will be instructed to notify study staff immediately. A phone number will be provided. Clinical examination post-procedure will be at Bascom Palmer Eye Institute.

Outcomes Measured

Primary outcome:

Outcome Measure Title: Change in palpebral fissure height

Outcome Measure Description: Palpebral fissure height will be calculated from the sum of marginal reflex distance 1 and 2 measured from the photograph by Ipad software and recorded by investigators.

Outcome Measure Timeframe: Baseline prior to drop administration, Day 1

Secondary outcomes:

Outcome Measure Title: Change in eye redness

Outcome Measure Description: Scoring of ocular redness from clinical photographs will be performed by investigators on a 0 - 100 unit scale as compared to standardized reference photographs (0 = no redness, 100 = very red). Images may also be analyzed quantitatively using software to calculate changes in redness between photographs.

Outcome Measure Timeframe: Baseline prior to drop administration, Day 1

Outcome Measure Title: Change in Patient-reported eye appearance

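### The photographs behind the redness outcome have no stated white-balance or gain control and no colour reference; a reference card and a between-arm comparison of change would be a cheap improvement

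*Combined protocol and SAP*

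**What the plan says.** The imaging set-up is in Procedures Involved, Part 1. On the room: "Images will be taken in a room with the same conditions". On geometry: "This app directs subjects to a standardized position and distance from the Ipad to measure the MRD1 and MRD2 in each eye". On the camera: "All photographs will be taken with the dedicated Ipad camera, which will use standardized aperture, shutter speed, and exposure time". On the file: "Photographs will be recorded and saved as JPG files (1200 9 797 pixels, 24-bit, RGB) in a locked folder" (the 9 is most likely a misread multiplication sign). Part 3 repeats the set-up after treatment: "Subjects will be photographed at 2 hours after drop instillation according to the procedure described above".

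Under Outcomes Measured, the secondary redness outcome rests on photographs: "Scoring of ocular redness from clinical photographs will be performed by investigators on a 0 - 100 unit scale as compared to standardized reference photographs". A second route is optional: "Images may also be analyzed quantitatively using software to calculate changes in redness between photographs". Part 4 adds: "User performing analysis will be blinded to which patients received study drug or control".

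The Statistical Analysis Plan section names a paired t-test for palpebral fissure height, redness and the FACE-Q score. It gives 114 subjects and a 0.05 significance level. White balance, gain and a colour target are not mentioned anywhere in the document.

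**The concern.** Redness is a colour measurement, but the imaging set-up is built around an app that measures lid distances. Shutter speed and exposure time are the same setting, so the camera sentence fixes two parameters, and both govern brightness. White balance, which sets the ratio of red to green and blue in the stored image, is not among them. The plan describes no other photographs from which redness could be scored.

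The outcome is a difference between two images taken 2 hours apart, so a colour shift in either image passes straight into it. A random shift widens the spread of redness change and costs power. A systematic shift between the first and second image could look like a drug effect if the analysis is done within one arm. Redness in healthy eyes is one of the questions the Background presents as not yet evaluated, so avoidable noise in it is worth removing.

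**Working it through.** **1. What is and is not fixed.** Stated as standardized: device, room conditions, position, distance, aperture, shutter speed/exposure time. Not stated: white balance, gain, colour reference, light level or colour temperature, and whether any file other than the JPG is kept.

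**2. How a colour shift enters a software measure (assumed values).** Take a simple index, the red fraction R/(R+G+B), with assumed scleral values 200/190/180.
- No drift: 200/570 = 0.3509.
- Red channel up 5%: 210/580 = 0.3621, a change of +0.011.
- Red channel up 10%: 220/590 = 0.3729, a change of +0.022.
- All channels scaled by the same factor k: 200k/570k = 0.3509, no change.

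For this index, channel-specific drift (white balance) is what matters; uniform gain affects brightness. With a card in the frame, the same 5% drift raises the card's red reading by 5%, and dividing it out gives 210/1.05 = 200. The 0.011 cannot be converted to the 0–100 investigator score, because the documents give no link between the two.

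**3. The plan's sample size.** The 114 cannot be reproduced: no effect size, SD, power, sidedness or allocation ratio is given. By back-calculation (assuming 1:1, two-sided 0.05, normal approximation), 57 per arm has 80% power for d = (1.960 + 0.842) × √(2/57) = 0.525 SD of change. This serves only as a reference point below.

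**4. Random shift, between-arm comparison.** Let r be the ratio of camera variance in the change score to all its other variance. Then power = Φ(d√(57/2)/√(1+r) − 1.960), with d√(57/2) = 2.802. The total N that restores 80% is twice 57(1+r), with 57(1+r) rounded up.

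| r (assumed) | Power | N for 80% |
|---|---|---|
| 0 | 0.80 | 114 |
| 0.10 | 0.76 | 126 |
| 0.25 | 0.71 | 144 |
| 0.50 | 0.63 | 172 |
| 1.00 | 0.51 | 228 |

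If the error is unrelated to arm, the estimated difference between arms is not biased.

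**5. Systematic shift between first and second image.** Let b be a common shift and δ the drug effect on change relative to saline. Expected change is δ + b on drug and b on saline (setting any saline effect to zero). The between-arm difference is (δ + b) − b = δ, so the shift cancels. A within-arm paired t-test on drug estimates δ + b. With n = 57, δ = 0 and b in SD units of change, the rejection rate is Φ(b√57 − 1.960) + Φ(−b√57 − 1.960).

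| b (assumed) | b√57 | False-positive rate |
|---|---|---|
| 0 | 0 | 0.05 |
| 0.1 | 0.755 | 0.12 |
| 0.2 | 1.510 | 0.33 |
| 0.3 | 2.265 | 0.62 |

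**The case against.** The set-up is tighter than the camera sentence alone suggests. One dedicated device, the same room conditions, a directed position and distance, and a repeat of the same procedure at 2 hours are all protections against colour drift. The analyst is blinded to arm, and there is a randomized saline group. The specified outcome is a human score against reference photographs, which probably depends less on colour balance than a pixel calculation does. Software analysis is optional. All of this stands and limits the likely size of the problem.

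Three stronger readings are tempting, and the documents do not support them.
- A reader might infer that colour balance is left on automatic. The plan is silent on it; what the app does with white balance and gain is not described.
- A reader might infer that the error could never be removed afterwards, or that the JPG format and pixel count defeat the outcome. Partial normalisation of a JPG is possible, a card in the frame would make it more reliable even in a JPG, and a common shift cancels between arms. The plan does not say that originals are discarded, and no vessel-level measurement is planned that would set a resolution requirement.
- A reader might infer that camera error biases the trial's redness result. Random error unrelated to arm costs precision only. Imitation of an effect needs a systematic shift together with a within-arm test.

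What remains is that the protocol lists the settings it standardizes, and the one bearing most directly on colour is absent, as is any reference that would allow a check.

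**Conclusion.** The point holds as a modest measurement gap in a secondary outcome. The photographs supplying redness change have no specified control of white balance or gain and no colour reference. Any resulting colour shift would add noise to redness change, most directly in the optional software measure. The primary outcome is a distance and is unaffected.

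The size is unknown: the documents give neither a camera error nor an SD for redness change. The power and false-positive figures above rest on assumed variance ratios and shifts, 1:1 allocation, two-sided 0.05 and a normal approximation. They show the direction and what would be at stake, not an estimate for this trial. The within-arm figures also assume that the paired t-test pairs baseline with 2 hours; the SAP does not define the pairs, but a paired test cannot contrast two separate groups of subjects.

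**What to change.** In Procedures Involved, Part 1, and by reference Part 3:
- Place a small grey or colour reference card in every frame and normalise each image to it before investigator grading or software analysis. Check beforehand that the card does not disturb the app's distance measurements.
- Lock white balance and gain if the app allows, and record their values for both images.
- Keep the original file if the app provides one, alongside the JPG.

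In the Statistical Analysis Plan section, make the redness analysis a comparison of change between the oxymetazoline and saline arms, with the within-arm paired t-test descriptive at most.

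The cost is a printed card, slightly longer image processing and more storage, with no extra visits, staff or subjects. The card and settings must be in place before imaging, because a missing reference cannot be added later. For images already taken, the between-arm analysis is still available.

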Title: The effect of Upneeq (oxymetazoline hydrochloride 0.1%) on palpebral fissure height, eye redness, and patient-reported eye appearance.

UMH Protocol Number: 20210199

NCT04831047

3/29/23

Protocol Title

The effect of Upneeq[™] (oxymetazoline hydrochloride 0.1%) on palpebral fissure height, eye redness, and patient-reported eye appearance.

Objectives

Aim 1:

To determine the effect of Upneeq[™] (oxymetazoline hydrochloride 0.1%) on palpebral fissure height.

Aim 2:

To determine the effect of Upneeq[™] (oxymetazoline hydrochloride 0.1%) on eye redness.

Aim 3: To evaluate the effect of Upneeq[™] (oxymetazoline hydrochloride 0.1%) on patient-reported eye appearance.

Hypothesis: We hypothesize application of Upneeq[™] (oxymetazoline hydrochloride 0.1%) will cause an increase in subjects' palpebral fissure height, decrease in eye redness, and improvement in patient-reported eye appearance.

Background

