The study coordinator will assign each patient a specific ID number and place this information on a separate spreadsheet. The study coordinator will collect the sex, patient's age, and dates of service, but no other identifiable information. No names will be used in the forms. Presentations and publications will not identify individual patients. Data from the subjects' medical records will be encrypted and stored securely as detailed below. Identifiable data will not be stored for future use beyond the timeframe of this study. The release of data will be only to study members and no other outside organization. Data will be kept under lock and key in [name] office at the Bascom Palmer Eye Institute Oculoplastics Research Laboratory on the 4th floor ([name]), data encoded in the computer will be password-protected and will be available only to study personnel, and protected health information will not be re-used or disclosed for other purposes. Study members will be trained on how to log in and log out of the computers. The study coordinator will assign each patient a specific ID number and the sex, patient's age and date of on a separate spreadsheet. The study coordinator will record the study results with the specific sample ID on another spreadsheet.

Statistical Analysis Plan

Statistical analysis will be performed by the researchers. A paired t-test will be used to analyze the difference in palpebral fissure height, eye redness, and patient-reported eye appearance as measured through the FACE-Q survey. 114 subjects will be required to perform perimetric statistics. Chi-squared testing will be used to assess categorical variables. P <0.05 will be considered significant.

Risks to Subjects*

The primary risks to the subjects are adverse reactions to the medication. These risks are explained to patients prior to their arrival to the Oculoplastics Clinic. Previously described potential adverse reactions to include instillation site discomfort, punctate keratitis, and blurry vision although in general is well-tolerated.^{21–23,33} Potential psychosocial risks to subjects include time taken from their day to undergo tests, potentially missing work, and anxiety or discomfort from the eye drop instillation process. This study is not collecting sensitive information, thus no potential risk to reputation or legal risks should occur.

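### The paired t-test named for redness and FACE-Q does not compare drug with saline, and no masking of redness graders to time point is specified

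*Combined protocol and SAP*

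**What the plan says.** **Design.** Under Procedures Involved, Part 2, subjects are randomised to the drug or to saline, given to both eyes. Photographs and surveys are taken at baseline and again two hours after the drop.

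**Test.** The Statistical Analysis Plan states: "A paired t-test will be used to analyze the difference in palpebral fissure height, eye redness, and patient-reported eye appearance". Chi-squared testing is named for categorical variables, and significance is set at 0.05. No between-arm test of a continuous score is named.

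**Masking.** Procedures Involved, Part 4 states: "User performing analysis will be blinded to which patients received study drug or control". The same list includes "investigator-assessed measurements of conjunctival color including the Validated Bulbar Redness Scale", so the rule probably reaches the people who grade redness. Neither viewing order nor hiding of the before/after label is mentioned.

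**Grading.** Under Outcomes Measured, redness scoring is "performed by investigators on a 0 - 100 unit scale as compared to standardized reference photographs". A software measure is optional: "Images may also be analyzed quantitatively using software to calculate changes in redness between photographs".

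**Expectation.** The hypothesis under Objectives is an increase in "palpebral fissure height, decrease in eye redness, and improvement in patient-reported eye appearance".

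**The concern.** A paired test asks whether scores after the drop differ from scores before it. That difference mixes the drug effect with everything else that changes over two hours: the effect of instilling any drop, the passage of time, a placebo response on the FACE-Q, and any tendency of a grader to score the later photograph as less red. The randomised saline arm is there to separate these, but the named test does not use it.

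Masking to arm does not protect a before/after contrast, because before versus after is the dimension on which no masking is specified. A significant fall in redness or gain in FACE-Q score could be reported as a drug effect when saline would have produced the same.

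**Working it through.** **Inputs.** From the documents: 114 subjects in total, two arms, two time points, alpha 0.05. Assumed because the documents do not say: 1:1 allocation (57 per arm), two-sided testing, one value per subject, no true drug effect, and the shift sizes. The documents give no SD, effect size or power, so 114 cannot be reproduced and there is no planned power figure to check against. Shifts are in units of the SD of the change, in the favourable direction.

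**1. Paired test in one arm of 57.** With a shift of d SD, the t statistic is noncentral t on 56 degrees of freedom with noncentrality d × √57 = 7.550d. The critical value is 2.003.

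| Shift d | Noncentrality | Favourable significant result |
|---|---|---|
| 0 | 0 | 2.5% |
| 0.1 | 0.755 | 11.2% |
| 0.2 | 1.510 | 31.7% |
| 0.3 | 2.265 | 60.5% |

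The cause of the shift makes no difference to the arithmetic. A FACE-Q placebo response of the same SD size gives the same percentages, whether or not arm is masked. If the SD of change in redness were 10 points (assumed; range 5 to 15), the three shifts would be 1, 2 and 3 points on the 0-100 scale (ranges 0.5-1.5, 1-3 and 1.5-4.5).

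**2. Between-arm test, shift shared by both arms.** The expected difference in mean change is d − d = 0, so the favourable rate stays at its nominal 2.5%. A simulation of 40,000 runs gave 0.025 at each of the three shifts.

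**3. Between-arm test, shift in the drug arm only.** This would arise if graders could tell treated eyes apart. If a fraction f of the drug arm is shifted by d, the noncentrality is f × d × √(57/2) = 5.339fd on 112 degrees of freedom, with critical value 1.981.

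- d = 0.3 and f = 0.25, 0.5 or 1: 5.9%, 12.2% or 35.5%.
- d = 0.2 and the same fractions: 4.5%, 7.6% or 18.4%.

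The between-arm test does not remove this part. The documents give nothing from which to estimate f.

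**4. Sensitivity given up.** Solving the same distributions for 80% power gives 0.378 SD for the paired test (n = 57) and 0.529 SD for the two-sample test on change (57 per arm). The two figures refer to different quantities: the first is total change, the second is drug minus saline.

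**5. Workload.** 114 × 2 = 228 photographs. At an assumed 1-2 minutes each this is 228-456 minutes, or 3.8-7.6 hours. Single-eye crops would number 228 × 2 = 456, or 7.6-15.2 hours.

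**The case against.** The best defence is that the plan already contains real safeguards. Analysis is masked to arm, redness is anchored to reference photographs, camera settings are fixed, and a coordinator already assigns ID numbers and records results under them (Data Management). Redness and FACE-Q are secondary outcomes, and the study calls itself a pilot (Local Number of Subjects). Every shift size above is assumed. All of this stands and limits the weight of the point. None of it makes a paired test a comparison of drug with saline.

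A second objection also stands: the 11%, 32% and 60% figures argue mainly for changing the analysis. If arm masking covers the graders and works, a shared shift cancels once the arms are compared, and masking to time point then mainly protects the paired results kept as description.

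A reader might go further in three ways that the documents do not support:

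- **That graders are known to see the time point.** The documents are silent. They do not say that photographs are shown labelled or in before/after pairs.
- **That visible lid lift reveals the arm, so cropping is essential.** The photographs do serve to measure lid position, so a cue is possible. However, the Background says that benefit in mild or minimal lid malposition has not been evaluated. Once single images are shown in random order, the grader no longer has the subject's own baseline alongside. The size of any remaining cue is unknown, and cropping cannot hide whitening, which is the outcome itself.
- **That staffing rules out better masking.** Resources Available lists resident physicians and a research fellow. The stated time and resource limit explains the number of participants.

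**Conclusion.** The point holds as a gap in the analysis plan together with an unspecified detail of masking. As written, the test for redness and FACE-Q scores cannot separate a drug effect from a grading, time or placebo shift. Under the stated assumptions, a shift of 0.2 SD is enough to raise the chance of a falsely favourable result from 2.5% to about 32%. A between-arm comparison restores 2.5% for any shift that both arms share. It does not do so for a shift confined to the drug arm, which is the reason to strengthen masking of the graders as well.

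The percentages are illustrations and do not estimate bias in this trial. The structural point, that the named test leaves out the saline arm, needs no assumption about shift size. It should be corrected, with weight in proportion to two secondary outcomes in a pilot.

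**What to change.** **Main change (Statistical Analysis Plan).** State that the change in redness and in FACE-Q score will be compared between arms, by ANCOVA with the baseline score as covariate or by a two-sample t-test on change. Keep paired results within each arm as description. Cost: no extra subjects or procedures, but the difference detectable with 80% power rises from 0.38 SD (paired, 57 subjects) to 0.53 SD (two-sample on change, 57 per arm).

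**Supporting change (Procedures Involved, Part 4).** State that the masking rule covers the redness graders. Extend the existing ID coding so that they see the saved photographs one at a time in random order, with time point, date and arm hidden. Cost: about 4-8 hours of image handling for 228 photographs at the assumed 1-2 minutes each, excluding grading time. Single viewing may also add noise compared with side-by-side grading.

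**Optional.** Crop to the conjunctiva, if a trial run shows that the crops can still be scored against the reference photographs. This may weaken a lid-position cue. With single-eye crops, image handling would come to about 8-15 hours in total.

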Outcome Measure Description: Patient-reported eye appearance will be assessed by patient completion of the FACE-Q Eye Module Survey. These surveys have a total raw score of 7 (worst) to 28 (best). Higher scores indicate greater satisfaction. These survey scores will be

assessed individually. Additionally patients will be queried regarding their perception of the drop including changes in eye appearance before or after drop instillation. Outcome Measure Timeframe: Baseline prior to drop administration, Day 1

Adverse Events and Serious Adverse Events

Treatment-emergent adverse events, defined as any event not present prior to the initiation of the drug treatment or any event already present that worsens in either intensity or frequency following exposure to the drug treatment, will be monitored and reported throughout the study. Treatment emergent adverse scale will be graded as the following:

- Mild: Transient or mild discomfort (<48 hours) to the subject; no medical intervention/therapy required.

- Moderate: Mild to moderate limitation in activity of the subject; no or minimal medical intervention/therapy required.

- Severe: Marked limitation in activity of the subject, some assistance usually required; medical intervention/therapy required including possible hospitalization.

Serious adverse events are defined as those which result in death, hospitalization, persistent or significant incapacity or substantial disruption of the ability to conduct normal life functions (aka disability), or congenital anomaly / birth defect.

Previously reported treatment-emergent adverse effects are described further in the risks section below.

Withdrawal of Subjects

Patients may withdraw at any time at their discretion. Subject withdrawn from and/or terminated from research with or without their consent are those who are found to not meet inclusion/exclusion criteria, and/or are not able to complete the research protocol in its entirety, as well as those who suffer a treatment-emergent adverse effect requiring medication discontinuation. For any subjects who withdraw from research, including partial withdrawal from procedures, study data of the withdrawn subject will not be included in statistical analysis and will be shredded.

Data and Specimen Banking*

Not applicable.

Data Management*

Steps to Secure Data

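### Blinding is stated only for the user performing the analysis, which leaves the redness score and the FACE-Q self-rating open to bias

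*Combined protocol and SAP*

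**What the plan says.** The only blinding statement about this trial is in Procedures Involved, Part 4: "User performing analysis will be blinded to which patients received study drug or control". The rest of the plan bears on it as follows.

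- **Treatment (Part 2).** Subjects are randomised to Upneeq or "balanced saline placebo in both eyes". "Based on the randomization results, the examiner will apply" one or the other. No coded supply, matched container or separate dispenser is described.
- **Redness (Outcomes Measured, secondary outcomes).** "Scoring of ocular redness from clinical photographs will be performed by investigators on a 0 - 100 unit scale", against reference photographs. A software measure is optional: "Images may also be analyzed quantitatively using software to calculate changes in redness between photographs".
- **Redness again (Part 4).** The data to be assessed include "investigator-assessed measurements of conjunctival color including the Validated Bulbar Redness Scale". This item sits directly above the blinding sentence.
- **Appearance (Outcomes Measured, secondary outcomes).** "Patient-reported eye appearance will be assessed by patient completion of the FACE-Q Eye Module Survey". Subjects are also asked how they perceived the drop.
- **Palpebral fissure height (primary outcome).** This is the sum of MRD1 and MRD2, measured by the iPad software from the photograph and entered by investigators.
- **Analysis (Statistical Analysis Plan).** The researchers carry out the analysis, using a paired t-test for all three outcomes.

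**The concern.** Blinding at the analysis stage cannot remove bias that entered when the data were generated. The redness score is a human judgement on a 0 to 100 scale, and FACE-Q is a self-rating. Either can drift if the person giving the score knows or guesses the treatment.

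Knowledge of the time point matters as well. If the paired test compares each subject before and after the drop, a scorer who knows which image is the later one can produce an apparent change in both arms. That error cancels in a comparison between arms only if the scorer does not know the arm. It does not cancel in a within-subject test.

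Redness and patient-reported appearance are two of the three stated aims. The Background presents the trial as supplying randomised evidence on redness that does not yet exist, so a positive redness result would carry weight.

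**Working it through.** **Step 1: which roles are covered.** I set each role beside what the text says about it.

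| Role | Sees or does | Blinding stated? |
|---|---|---|
| Subject | Receives the drop, completes FACE-Q | No; the word placebo suggests intent only |
| Examiner | Applies the drop according to the randomisation result | No |
| Photographer | Takes baseline and 2-hour images | No; role not assigned |
| Redness scorer | Scores photographs from 0 to 100 | Only if this person is the Part 4 user |
| Person running the analysis | Analyses the data | Yes |

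No passage says that these roles are held by different people, and none says that they are held by the same person. No passage says that photographs are stripped of their date, order or subject identity before scoring.

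**Step 2: exposure of each outcome.**
- FACE-Q depends on the subject, whose blinding is not stated on any reading of Part 4.
- Redness depends on the scorer. On the narrow reading of Part 4 the scorer is unmasked to both arm and time point. On the generous reading the scorer is masked to arm but still not to time point.
- Fissure height is computed by software from images taken at a position and distance set by the app, in primary gaze, with fixed camera settings. Little judgement remains.

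**Step 3: what a given bias would do.** The plan states no figure for bias, so there is nothing of its own to reproduce. The plan supplies 114 subjects and a 0.05 significance level. I assume 1:1 allocation, so 114 / 2 = 57 per arm, a two-sided two-sample t-test, and no true effect. Let b be the arm-related shift in SD units.

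- Standard error of the difference, in SD units: √(2/57) = 0.187
- Degrees of freedom: 114 − 2 = 112, giving a critical value of 1.981
- Noncentrality: b / 0.187
- Rejection probability: P(|T| > 1.981), with T noncentral t

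| b (assumed) | Noncentrality | Noncentral t | Normal approximation |
|---|---|---|---|
| 0 | 0 | 5.0% | 5.0% |
| 0.1 | 0.534 | 8.3% | 8.3% |
| 0.2 | 1.068 | 18.5% | 18.7% |
| 0.3 | 1.602 | 35.5% | 36.0% |

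The normal approximation is Φ(b/0.187 − 1.96) + Φ(−b/0.187 − 1.96). These figures would be the same for any comparison of 57 with 57. They show how sensitive such a comparison is to a shift, not how large a shift to expect here.

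**The case against.** The strongest reply is that silence is not proof of an unblinded trial, and much of that reply stands.

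- **The blinded user may be the redness scorer.** Part 4 lists the redness assessment immediately above the blinding sentence, and scoring is done from saved images. A reader might infer that only a data analyst is blinded, but the text does not settle this. The outcome definition, however, assigns scoring to investigators without mentioning blinding, and no reading covers the time point.
- **The examiner's knowledge of the arm is an inference.** Acting on the randomisation result is the natural route to knowing the arm, but the sentence is also compatible with coded drops. Nor do the documents say that the examiner photographs or scores.
- **The control is called a placebo.** This points to intended masking of subjects. The consent form is not in the public document, so what subjects are told cannot be checked. The word still supplies no procedure.
- **The primary outcome.** A reader might extend the concern to fissure height through the way photographs are taken. The standardised capture and software measurement count against that, and the documents describe nothing that would give it force.
- **The survey.** Part 3 describes it as asking about change after Upneeq, although one arm gets saline. A reader might infer a leading questionnaire. That sentence is the protocol's own description, not the questionnaire text. FACE-Q is an existing instrument, and the added questions are described neutrally.
- **The magnitude.** The shifts are assumed, 1:1 allocation and two-sidedness are not stated, and the plan names a paired test rather than a two-sample test. The figures are illustrative only.

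What remains is that masking of subjects and of the instilling examiner is not ensured, masking of the scorer to arm is uncertain, and masking to time point is absent.

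**Conclusion.** The concern holds as a gap in protection for the two subjective secondary outcomes. It is not a finding that the trial is unblinded, and it does not seriously threaten the primary outcome. It is worth acting on because it goes beyond missing detail: coding and shuffling saved photographs and separating tasks would remove a bias that analyst blinding cannot reach.

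The size is unknown. Under the assumptions in the working, the false-positive rate rises from 5% to about 18.5% for a 0.2 SD shift and to about 35.5% for a 0.3 SD shift. Those figures are generic, and the documents offer no basis for choosing between them. No stated figure is contradicted, and the sample size does not change.

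**What to change.** Amend Procedures Involved, Parts 2 to 4, and the redness outcome definition as follows.

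1. Before scoring, relabel the saved photographs with random codes and shuffle them, so that the redness scorer sees neither arm nor time point.
2. State that the person who instils the drop does not score redness and, where staffing allows, does not take the 2-hour photographs or record MRD values.
3. State that subjects are not told their arm and are not shown the product until the post-treatment survey is complete.
4. Have the allocation code held by a team member who neither records results nor scores outcomes. This rules out the study coordinator, who records the study results under Data Management.

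The cost is protocol wording, a coding list and separation of tasks at each visit. The resident physicians and research fellow listed under Resources Available could share the roles, so no new assessor is needed. The practical burden is that more than one team member must be available at each visit.
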